4.4. Safety Analyses

All safety tabulations will be presented by treatment and dose and separately by concentration for all subjects in the Safety population.

If warranted, additional analyses of safety versus PK exposure (eg, AUC and C_{max}) may be explored.

4.4.1. Study Drug Exposure

Study drug exposure will be calculated as the number of days subjects were administered study drug, as determined below, using descriptive statistics.

$$\text{Duration of Study Drug Exposure (days)} = (\text{Date of last dose} - \text{Date of first dose}) + 1$$

Dose intensity will be computed using the following definition and summarized by treatment and dose and separately by concentration:

$$\text{Dose Intensity} = \frac{\text{Cumulative Actual Dose}}{\text{Actual Treatment Duration}}$$

Relative dose intensity will be computed using the following definition and summarized by treatment and dose and separately by concentration:

$$\text{Relative Dose Intensity (\%)} = \frac{(\text{Cumulative Actual Dose} / \text{Actual Treatment Duration})}{(\text{Cumulative Planned Dose} / \text{Planned Treatment Duration})} * 100$$

Percent compliance will be summarized for each subject as:

$$\text{Percent Compliance (\%)} = \frac{\text{Number of Injections Received}}{\text{Number of Injections Expected}} * 100$$

The number of injections expected is the number defined in the protocol (9 total injections per subject). The number of expected injections for any subject who withdraws or dies prior to completing all scheduled doses will be counted up to the date of withdrawal or death.

Duration of study drug exposure, number of doses received, dose intensity, relative dose intensity, and percent compliance for each subject will be listed by cohort.

4.4.2. Adverse Events

All AEs will be coded using the MedDRA coding system and displayed in tables and data listings using system organ class (SOC) and preferred term (PT). AEs will be presented by severity (mild, moderate, or severe).

Analyses of AEs will be performed for those events that are considered treatment-emergent, where treatment-emergent is defined as any AE occurring after the first dose of study medication. Adverse events reported prior to dosing will be considered non treatment-emergent.

The number and percentage of subjects as well as the number of events for each particular treatment-emergent AE (TEAE) will be summarized by treatment and dose, concentration, SOC, and PT for the following: TEAEs, TEAEs assessed by the Investigator as related to treatment, severe TEAEs, serious TEAEs, TEAEs leading to permanent study drug discontinuation, TEAEs leading to temporary discontinuation, TEAEs leading to dose reduction, TEAEs by maximum severity, and TEAEs by relationship to study drug.

In these tabulations for the number and percentage of subjects, each subject will contribute only once (i.e., the most related occurrence or the most intense occurrence) to each of the incidence rates for a given SOC or PT in the descriptive analysis, regardless of the number of episodes.

For tabulations that include classification by relationship to study treatment, AEs with missing relationship will be considered related to study drug. For tabulations that include classification

by severity, AEs with missing severity will be included in a category for missing.

All AEs occurring on-study will be listed in by-subject data listings by cohort.

By-subject data listings will also be provided for the following: subject deaths, SAEs, severe TEAEs, TEAEs leading to treatment discontinuation, and TEAEs leading to dose reduction.

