### 7.3. Safety Evaluations

#### 7.3.1. Adverse Events (AEs)

Adverse events will be collected continuously starting from signing the Informed Consent Form (ICF) until EOS visit for randomized subjects.

Adverse events reported prior to dosing will be considered non treatment emergent. Any new systemic effect that occurs between scheduled visits should be brought to the attention of the Investigator and recorded in the subject's files.

Common Terminology Criteria for Adverse Events (CTCAE) will be used to determine the AE safety profile of ELX-02. For more information refer to Section 8.

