3.10. Missing, Unused, and Spurious Data

In general, there will be no substitutions made to accommodate missing data points, other than described in this section. All data recorded on the eCRF will be included in data listings.

When tabulating AE data, partial dates will be handled as follows. If the day of the month is missing, the onset day will be set to the first day of the month unless it is the same month and year as study treatment. In this case, in order to conservatively report the event as treatment-emergent, the onset date will be assumed to be the date of first dose. If the onset day and month are both missing, the day and month will be assumed to be January 1, unless the event occurred in the same year as the study treatment. In this case, the event onset will be coded to the date of first dose in order to conservatively report the event as treatment-emergent. A missing onset date will be coded as the date of first dose. If the resulting onset date is after a reported date of resolution, the onset date will be set equal to the date of resolution. Imputation of partial dates is used only to determine whether an event is treatment-emergent; data listings will present the partial date as recorded in the eCRF.

Missing AE severities will not be imputed and will be considered missing in any tabulations of AE severity. When relation of AE to the study drug is missing, the AE will be considered “related” to study drug.

When tabulating concomitant medications, if an end date is missing or the medication is ongoing at the time of first dose, the medication will be considered concomitant.

All final PK parameters will be calculated based on actual time from dose. Interim PK parameters may be calculated based upon scheduled time if actual time data are not yet available.

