4.4.4. Laboratory Data

Clinical laboratory values will be expressed in Système International (SI) units.

The actual value and change from baseline (Day 1) to each on-study evaluation will be summarized for each clinical laboratory parameter, including hematology, clinical chemistry, urinalysis, and coagulation and presented by treatment and dose and separately by concentration. In the event of repeat values, the last non-missing value per study day/time will be used. Laboratory results recorded at unscheduled visits will not be tabulated.

Severity of clinical laboratory measurements will be determined using Common Terminology Criteria for Adverse Events (CTCAE) criteria when available.

Shift tables of change in CTCAE grade of laboratory parameters from baseline to worst value and from baseline to last value on study will be presented. Both scheduled and unscheduled visits will be included in shift tables.

All laboratory data will be provided in by-subject data listings, including results of pregnancy tests, alcohol tests, and serology. A subset listing will be presented for all laboratory values with CTCAE grade ≥ 3 .

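### The TEAE definition has no worsening clause, so a symptom present at first dose that worsens on drug can be left out of every TEAE table

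*SAP*

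**What the plan says.** SAP section 4.4.2 sets the scope of the AE tables: "Analyses of AEs will be performed for those events that are considered treatment-emergent". It then gives the definition, "treatment-emergent is defined as any AE occurring after the first dose of study medication", and closes off anything earlier: "Adverse events reported prior to dosing will be considered non treatment-emergent". Protocol section 7.3.1 carries the same rule: "Adverse events reported prior to dosing will be considered non treatment emergent".

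Predose events will be in the database, because Protocol section 7.3.1 also says: "Adverse events will be collected continuously starting from signing the Informed Consent Form (ICF) until EOS visit for randomized subjects".

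Every table named in SAP 4.4.2 is a TEAE table: overall, related, severe, serious, leading to permanent or temporary discontinuation, leading to dose reduction, by maximum severity and by relationship. Three of the special listings (severe events, events leading to treatment discontinuation, events leading to dose reduction) are also limited to TEAEs. The death and SAE listings are not, and there is a general listing: "All AEs occurring on-study will be listed in by-subject data listings by cohort". SAP section 4.4.3 assesses AEs of interest as treatment-emergent events in its summary but lists all on-study AEOIs.

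SAP section 5, on changes to the planned analyses, does not mention the TEAE definition.

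**The concern.** A treatment-emergent definition is meant to separate what could be due to the drug from what could not. Onset before dosing makes the drug an unlikely cause of the event's start. It says nothing about a later increase in severity, which is a possible drug effect in the same way as a new event. A definition that looks only at timing of first report discards that information.

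The incidence and characteristics of AEs form a primary endpoint (Protocol section 2.2.1), and the TEAE tables are where that endpoint is summarised by dose. If worsening is left out, a reader of the severe-TEAE or maximum-severity table at a given dose could see no severe event when one occurred on drug.

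The choice also runs against the SAP's stance elsewhere. In section 3.10, uncertain onset dates are resolved towards treatment emergence and missing causality is counted as related. Both are deliberately conservative; leaving out on-drug worsening is not.

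**Working it through.** The plan gives no figure to reproduce. The check is to apply the rule as written, look for any other text that rescues the event, and then size one occurrence.

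**Step 1. Apply the rule.** Take a headache reported as mild on Day -1, ongoing at first dose, severe on Day 5, and kept on one AE record.
- Reported before dosing? Yes, so it is not treatment-emergent under SAP 4.4.2.
- Counted in the severe-TEAE or maximum-severity table, or shown in the severe-TEAE listing? No.
- Shown in the all-AE listing? Yes. In the SAE or death listing? Only if it qualifies.

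**Step 2. Look for a rescue in the text.**
- Protocol section 8.20 (recording) and section 8.21.2 (CRF reporting) do not call for a new AE record when severity rises.
- SAP section 3.10 deals only with missing or partial onset dates: "Imputation of partial dates is used only to determine whether an event is treatment-emergent". A known predose onset is untouched by it.
- The outcome therefore depends on site practice. If a site opened a new record at the change in severity, that record would be a TEAE. If it updated the existing record, the worsening is lost from the tables. Neither document says which applies.

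**Step 3. Can such events exist?** Collection starts at consent, and screening may be up to 42 days before dosing (Protocol section 7.1). Eligibility excludes persistent tinnitus or dizziness, but an acute condition excludes only if it falls within 48 hours of study start and is judged significant (Protocol section 4.2). A mild headache at first dose is compatible with entry. Headache was among the commonest TEAEs in the pooled single-dose studies (5 subjects, 8%; Protocol section 1.2.2). This shows that the case is possible, not how frequent it is.

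**Step 4. Size of one occurrence.** Inputs: 6 ELX-02 and 3 placebo subjects per cohort over seven cohorts (SAP section 1.2.1); 1.0 mg/kg given in Cohorts 3 and 5, and 2.5 mg/kg in Cohorts 4 and 6; placebo pooled (SAP section 3.2). Change in incidence = 1/n, using planned numbers.

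| Column | n | Change from one subject |
|---|---|---|
| 0.1, 0.3 or 5.0 mg/kg (one cohort each) | 6 | 0/6 to 1/6 = 16.7 points |
| 1.0 or 2.5 mg/kg (two cohorts each) | 2 × 6 = 12 | 0/12 to 1/12 = 8.3 points |
| All ELX-02 | 7 × 6 = 42 | 0/42 to 1/42 = 2.4 points |
| Pooled placebo | 7 × 3 = 21 | 0/21 to 1/21 = 4.8 points |

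The assumption of one affected subject is illustrative; the documents give no predose AE rate.

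**The case against.** The strongest reply is that little would be missed in practice. Much worsening has its own route into the tables:
- Laboratory values: "Shift tables of change in CTCAE grade of laboratory parameters from baseline to worst value" (SAP section 4.4.4).
- Hearing: significant change from baseline is tabulated (SAP section 4.4.6.2) and must itself be treated as an AE of interest (Protocol section 8.4.2).
- Tinnitus and dizziness: change and category shift on the THI and DHI (SAP sections 4.4.6.5 and 4.4.6.6).
- Vital signs and ECG: clinically significant changes become AEs (Protocol sections 7.3.3 and 7.3.5).

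The subjects are healthy, and eligibility is reconfirmed on Day -1 and Day 1. A symptom that resolves before dosing and then recurs is a new event anyway. All of this stands. It narrows the gap to symptomatic events such as headache, which have no parallel measure.

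Three stronger readings are tempting, and the documents do not support them.
- A reader might infer that DLT and MTD decisions are affected. They are not: Protocol section 3.2 counts subjects with graded drug-related toxicity, without reference to treatment emergence, and the DSMB reviews the safety data collected for each cohort (Protocol section 8.16).
- A reader might infer that the event disappears from the report. It does not, since the listings keep it.
- A reader might infer that such events are common because the predose window (up to 42 days) is about as long as Day 1 to the EOS visit (29 + 7 = Day 36 to 29 + 10 = Day 39). Window length shows opportunity only; 42 days is a maximum, and the event must also be ongoing at first dose, worsen, and stay on one record.

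**Conclusion.** The point holds as a reporting gap. As written, the SAP and protocol leave on-drug worsening of a predose symptomatic AE out of the tables that summarise the primary safety endpoint. The event can then be found only in by-subject listings.

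This rests on one assumption that the documents leave open: that worsening is kept on the original AE record. The number of affected subjects is unknown and may be zero. If there is one, the effect ranges from 2.4 points in the all-ELX-02 column to 16.7 points at a dose given in a single cohort. The larger figure applies at 5.0 mg/kg, the highest dose. The correction is worth making because it is cheap and the columns are small, not because the gap is shown to have changed any result or decision.

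**What to change.** In SAP section 4.4.2, define a TEAE as an AE with onset on or after the first dose, or an AE present before the first dose that increases in severity or becomes serious afterwards. Count such an event at its maximum post-dose severity. Remove or qualify the sentence that classes every predose report as non treatment-emergent, and record the departure from Protocol section 7.3.1 in SAP section 5.

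Apply the definition to the data already recorded. SAP section 1.2.1 already lists the final doses administered in all seven cohorts, so a protocol change to site recording would come too late. Where dated severity changes were not captured, review the predose AEs that were ongoing at first dose and flag in the listing those with evidence of worsening.

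The cost is a short SAP edit, a small data review, and possibly slightly higher TEAE counts in all groups, including placebo.

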4.4.3. Adverse Events of Interest and Injection Site Reactions

Treatment-emergent AEOIs, defined per-protocol as hypersensitivity, nephrotoxicity, and ototoxicity, will be assessed. AEOIs, searched by the following standardized MedDRA queries (SMQs), will be summarized by PT: Hypersensitivity, Hearing and Vestibular Disorders, and Acute Renal Failure, as appropriate. The number and percentage of subjects with at least one AEOI as well as the number of AEOIs will be presented by treatment and dose and separately by concentration.

ISRs, defined per-protocol as pain or tenderness, erythema or redness, induration or swelling, and pruritus, and assessed by the investigators according to the Division of Acquired Immunodeficiency Syndrome (DAIDS) Criteria as described in Protocol Section 13.1 will be summarized by grade at each timepoint.

ISRs reported as spontaneous AEs that are coded with the high-level term (HLT) “Injection site reactions” will also be analyzed. The number and percentage of subjects with at least one ISR as well as the number of ISR events will be presented by treatment and dose and separately by concentration. The duration of each reported ISR will be derived using the AE dataset. The average duration of ISRs per subject will be summarized by treatment and dose and separately by concentration.

All AEOIs and ISRs occurring on-study as well as the duration of each observed ISR will be listed in by-subject data listings by cohort.

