### End of Study Visit (Day 36)

This visit will take place 7-10 days after last dosing. Auditory and vestibular assessments may take place 7-11 days after last dosing.

The following assessments will take place:

- Physical examination.
- Assessment of local injection(s) reaction.
- Vital signs (supine BP, HR, RR, oral temperature).
- 12-lead ECG taken after 5 minutes in a supine position.
- Blood and urine safety tests.
- Serology (HIV, HBsAg, HCVAb).
- Urine pregnancy test (all women regardless of childbearing potential).
- Urine samples for creatinine and renal injury biomarkers.
- Serum alcohol test.
- Blood sampling for housekeeping proteins.
- AEs assessment and change in concomitant medications.
- Audiometry tests.
- Vestibular and tinnitus questionnaires.

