### **8.15. Follow-up of Adverse Events**

Subjects who have had an AE during the treatment period must be followed clinically until all parameters (including laboratory) have either returned to normal or have stabilized or are otherwise explained.

Any newly emergent SAE within 30 days after early discontinuation or study completion, that is considered to be related to the test drug or study participation should be recorded and reported immediately. The post-study period for the purpose of SAE reporting is until the SAE is resolved or stabilized or maximum up to 30 days following last visit of the study.

Unless decided otherwise, the study will terminate 30 days after last subject has attended the End-of Study visit. If additional follow-up of an AE is warranted, it will be documented in the as the subject' source data but will not be part of the CRF. The PI is required to report on any significant findings to the Sponsor.

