Revised Protocol	15 May 2018	
 
Following recommendations of the local (Belgium) Health Authorities, a cohort for administration of a 5.0 mg/kg dose could be implemented in this MAD study after satisfactory safety results were obtained for this dose in the SAD study. Results from the SAD study evaluating the ELX-02 5.0 mg/kg and 7.5 mg/kg SC doses were added to Section 1.2.2. Given the favorable safety profile of the doses, a dose cohort of 5.0 mg/kg was added to this MAD study.
 
Glomerular filtration rate was only meant to be an inclusion criterion and was carried through the protocol inadvertently. Use of the eGFR estimated by the MDRD equation to monitor acute changes in renal function in a normal population is not appropriate and not indicated because the MDRD equation applies only to subjects with a GFR below 60 ml/min, can never be used to assess acute renal changes, and depends on an equation that smooths out many critical parameters. We are measuring serum creatinines and KIM-1 and clusterin as parameters of renal function. Therefore, assessment eGFR estimated by the MDRD equation was removed from visits after the screening visit.
 
Sponsor address was changed.
 

Revised Protocol	24 September 2018	
 
Injection site reactions (ISR) have been observed for all cohorts completed to date. The completed cohorts and number of ISR are as follows: 0.1 mg/kg (2 subjects with 2 ISR), 0.3 mg/kg (7 subjects with 10 ISR), 1.0 mg/kg (5 subjects with 41 ISR) and 2.5 mg/kg (7 subjects
 

Document	Version Date	Summary of Changes and Rationale

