		
with 72 ISR). The 0.1 and 0.3 mg/kg cohort ISR were of short duration (maximum 2 weeks) compared to the 1.0 and 2.5 mg/kg cohorts (currently available data indicate ISR lasting up to 63 days). The events were generally mild, but the cumulative number of events in the 2.5 mg/kg cohort limit tolerability. The 0.1 and 0.3 mg/kg cohorts (50 mg/mL) were tolerated better than the 1.0 and 2.5 mg/kg doses (100mg/mL). In the 2.5 mg/kg cohort, one subject had a high frequency hearing change that met ASHA criteria. Therefore, an additional cohort of 2.5 mg/kg or 1 mg/kg at lower concentration (50 mg/mL instead of 100 mg/mL) is proposed. Adjustment to further cohorts may also be proposed depending upon the outcome of the repeated cohort.
 
 
• Additonal SC injection site locations are being allowed (e.g. thigh) to spread out the injection sites.
 
• Allowance for screening and baseline ENT exams to be performed on the same day to minimize subject burden
 

Section	Used to Read	Now Reads	Rationale for Change
Header  Date changed	24 SEPT 2018	8 NOV 2018	Changed to reflect new version
Cover Page	A Phase 1, Randomized, Double-Blinded, Placebo-Controlled, Third Party Open, Multiple Dose Escalation Study to Evaluate the Safety, Tolerability and Pharmacokinetics of Subcutaneously Administered ELX-02 in Independent	A Phase 1, Randomized, Double-Blinded, Placebo-Controlled, Third Party Open, Multiple Dose Escalation <del>Single Center</del> Study to Evaluate the Safety, Tolerability and Pharmacokinetics of Subcutaneously Administered ELX-02 in Independent	Protocol title has changed to reflect addition of new investigator, title has been changed throughout as appropriate

Section	Used to Read	Now Reads	Rationale for Change
	Consecutive Cohorts of Healthy Subjects	Consecutive Cohorts of Healthy Subjects	
	N/A	US IND Number: 137391	US IND Number added to expand the study to the USA
	N/A	To be determined, Investigator, USA	New investigator to be added in the USA

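### Injection site reaction duration is tabulated only as a per-subject average, with no rule for reactions that lack an end date

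*SAP*

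**What the plan says.** SAP 4.4.3 states: "The duration of each reported ISR will be derived using the AE dataset". The tabulated measure is then "The average duration of ISRs per subject will be summarized by treatment and dose and separately by concentration". Under SAP 3.2 a continuous variable is shown as n, mean, median, SD, minimum and maximum, so the maximum in this table is the largest subject average and not the longest reaction. Individual values appear only in listings: "as well as the duration of each observed ISR will be listed in by-subject data listings by cohort".

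On missing values SAP 3.10 says "In general, there will be no substitutions made to accommodate missing data points", apart from the exceptions it lists. Those exceptions cover AE onset dates and concomitant-medication end dates. AE end dates are not among them.

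On follow-up, Protocol 7.1 says of the EOS visit: "This visit will take place 7-10 days after last dosing". Protocol 7.3.1 collects AEs until that visit. Protocol 8.20 follows existing AEs until resolution, stabilisation or final database lock. Protocol 8.15 also requires clinical follow-up, and sets study termination, unless decided otherwise, at 30 days after the last subject's EOS visit. It then says that additional AE follow-up is kept in source data and "will not be part of the CRF".

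The Protocol 13.4 entry of 24 September 2018 gives ISR counts by cohort. It contrasts reactions of at most 2 weeks at 0.1 and 0.3 mg/kg with those at 1.0 and 2.5 mg/kg, where "currently available data indicate ISR lasting up to 63 days".

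**The concern.** Tolerability is a primary objective. The accumulated ISRs at 2.5 mg/kg are the sponsor's stated reason for adding a cohort at 50 instead of 100 mg/mL. In making that case the sponsor compared the longest reactions at each dose. The planned table does not report the longest reaction.

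A per-subject average treats a subject with many short reactions and one very long one much like a subject with moderate reactions throughout. If the number of reactions per subject rises with dose, so does the dilution, and the dose comparison is blunted where it matters most. The SAP uses worst-case conventions elsewhere (most intense AE occurrence in 4.4.2, worst laboratory value in 4.4.4) but not here.

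Separately, a reaction that is still open, or closed because it has stabilised, has no complete duration. With no stated rule, the programmer decides whether it is left out, cut at last contact, or closed at some other date.

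**Working it through.** **Inputs.** Last dose on Day 29 and EOS 7-10 days later (Protocol 7.1). Dosing on Days 1, 4, 8, 11, 15, 18, 22, 25 and 29. ISR counts and the 63-day figure from Protocol 13.4. Six active subjects per cohort (Protocol 3.1). The lengths of the shorter ISRs are my assumption (2, 7 or 14 days), because the documents do not give the distribution.

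**1. The 63-day figure on the visit schedule.** It is an observed value and cannot be recomputed, but it can be placed. EOS falls on Day 29 + 7 = 36 to Day 29 + 10 = 39. On the nominal schedule, time from onset to EOS is 35-38 days for a Day 1 reaction and 7-10 days for a Day 29 reaction. Since 63 - 38 = 25, that reaction was on record at least 25 days past EOS.

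**2. ISRs per affected subject.**

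| Dose (mg/kg) | ISRs / affected subjects | Ratio |
|---|---|---|
| 0.1 | 2 / 2 | 1.0 |
| 0.3 | 10 / 7 | 1.4 |
| 1.0 | 41 / 5 | 8.2 |
| 2.5 | 72 / 7 | 10.3 |

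Seven affected subjects exceed the six on active drug, so these counts appear to cover the whole blinded cohort. They show the order of magnitude and not an active-arm rate.

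**3. Dilution.** With k ISRs in a subject, one of 63 days and the rest of m days, the subject average is (63 + (k - 1)m) / k.

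| k | m = 2 | m = 7 | m = 14 |
|---|---|---|---|
| 8 | 77/8 = 9.6 | 112/8 = 14.0 | 161/8 = 20.1 |
| 10 | 81/10 = 8.1 | 126/10 = 12.6 | 189/10 = 18.9 |

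A low-dose subject with a single 14-day ISR averages 14 days, which is above the 8.1, 9.6 and 12.6 shown for a subject who had a 63-day reaction. Averaging again over six subjects, the other five at m days, gives (subject average + 5m) / 6. This runs from (8.1 + 10)/6 = 3.0 to (20.1 + 70)/6 = 15.0 days.

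**4. If the 63-day ISR has no end date and is left out,** the subject average becomes m: 2, 7 or 14 days.

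**5. Where an end date could fail to arrive.** Take the clause in Protocol 8.15 on follow-up outside the CRF as starting at study termination, 30 days after the last subject's EOS.
- For the last subject of Cohort 7, the time from a reaction on dosing day d to termination is (36 - d) + 30 to (39 - d) + 30. That is 65-68 days for Day 1, 62-65 for Day 4, 58-61 for Day 8 and 37-40 for Day 29. A 63-day reaction starting on Day 8 or later would still be open.
- For Cohort 6, at least 14 days pass from its last dose to Cohort 7's first, then 28 to Day 29, 7 to EOS and 30 to termination: 14 + 28 + 7 + 30 = 79 days. This exceeds 63, and earlier cohorts have longer.

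**The case against.** A fair defence has four parts. Follow-up of an existing AE does not stop at EOS: Protocol 8.20 carries it to resolution, stabilisation or lock, and the 63-day reaction shows that this happened at least once. Every ISR duration is listed by subject. DAIDS grades are summarised at each timepoint, and local reaction is assessed at EOS, so graded reactions present at that visit will be seen. Averaging within subject also keeps the subject as the unit of analysis, so a few subjects with many ISRs do not dominate a small descriptive table.

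Most of this stands, and it is a reason to keep the average. It does not answer the point. Listings do not compare doses or concentrations, an ISR without an end date has no defined duration to list, and a grade at EOS is not a duration.

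A reader might go further and infer that the longest reactions drop out because EOS comes so early. Cutting all data at Day 36-39, with exponential durations and onsets spread over the nine dosing days, makes true means of 10 and 30 days read as 7.0-7.5 and 10.3-11.2, so that a 3-fold difference looks like about 1.5-fold. The documents do not support that inference:
- EOS is not the cut-off for following an existing AE.
- The clause in Protocol 8.15 directly follows the sentence on study termination, and is most naturally read as applying after it.
- A 30-day exponential mean does not fit the sponsor's data. It gives P(duration > 63) = exp(-63/30) = 0.122, or about 14 of the 41 + 72 = 113 ISRs at 1.0 and 2.5 mg/kg, yet 63 days was the longest reported. (The sponsor called those data currently available, so some reactions may have run longer.)

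Nor does the SAP say that open ISRs are excluded. It is silent.

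**Conclusion.** The point holds in two parts.

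First, the only tabulated ISR duration is a per-subject average, and at the ISR frequency reported for 1.0 and 2.5 mg/kg it dilutes a long reaction heavily. One 63-day ISR among 8-10 gives a subject average of about 8 to 20 days if the others last 2 to 14 days. That range depends on the assumed short durations; the direction does not.

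Second, ISRs that are open, or closed as stabilised, have no defined duration. Leaving them out would shorten the reported duration. How many would be affected is not shown and cannot be worked out from the documents, which give no database lock date. The exposure is greatest in Cohort 7 (5.0 mg/kg), the highest dose and the last cohort, where the study ends about 30 days after EOS. The 50 versus 100 mg/mL tables use Cohorts 3 to 6 (SAP 3.2) and are less exposed, provided that late end dates for those cohorts reached the AE dataset.

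No error rate or sample size is involved. This is a gap in a descriptive table that bears on a primary objective, and it is worth closing before the table is produced.

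**What to change.** In SAP 4.4.3:
- Keep the per-subject average and add each subject's longest ISR duration, by dose and separately by concentration.
- State that an ISR without an end date, including one closed as stabilised, is right-censored at last contact and is not treated as missing. The AE outcome categories in Protocol 8.12 already separate resolved from unresolved events.
- Tabulate the number of subjects and of ISRs unresolved at EOS and at database lock.
- If a Kaplan-Meier summary is given, use one record per subject (the longest ISR) or allow for clustering within subject. A curve over individual ISRs would treat 8-10 correlated events per affected subject as independent.

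Reconcile Protocol 8.15 (additional follow-up outside the CRF) with 8.20 (follow-up to database lock), so that resolution dates obtained before lock enter the AE dataset.

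The cost is SAP wording, one extra table, and entry of dates from follow-up that is already required. Reported durations may become longer and less favourable. The longest ISR also tends to rise with the number of ISRs, so it should be read beside the counts that SAP 4.4.3 already tabulates.
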